## 2 PROTOCOL SYNOPSIS

Title	A Phase 3b, Randomized, Double-blind, Controlled Study Evaluating the Efficacy and Safety of VX-445/Tezacaftor/Ivacaftor in Cystic Fibrosis Subjects, Homozygous for F508del
Brief Title	A Study Evaluating the Efficacy and Safety of VX-445/Tezacaftor/Ivacaftor in Cystic Fibrosis Subjects, Homozygous for F508del
Clinical Phase and Clinical Study Type	Phase 3b, efficacy and safety
Objectives	
Primary Objective
 
To evaluate the efficacy of VX-445/tezacaftor (TEZ)/ivacaftor (IVA) in cystic fibrosis (CF) subjects, homozygous for F508del (F/F).
 
Secondary Objectives
 
 
• To evaluate the safety of VX-445/TEZ/IVA
 
• To evaluate the pharmacodynamics (PD) of VX-445/TEZ/IVA
 

Endpoints	
Primary Endpoint
 
 
• Absolute change in CF Questionnaire-Revised (CFQ-R) respiratory domain score from baseline through Week 24
 
 
Key Secondary Endpoint
 
 
• Absolute change in percent predicted forced expiratory volume in 1 second (ppFEV1) from baseline through Week 24
 
 
Secondary Endpoints
 
 
• Absolute change in sweat chloride (SwCl) from baseline through Week 24
 
• Safety and tolerability assessments based on adverse events (AEs), clinical laboratory values, ECGs, vital signs, and pulse oximetry
 

Number of Subjects	Up to approximately 158 subjects will be randomized (1:1) to either the VX-445/TEZ/IVA group or the TEZ/IVA group.
Study Population	Male and female CF subjects who are 12 years of age or older and have an F/F genotype
Investigational Drug	
During the TEZ/IVA Run-in Period, study drug refers to TEZ/IVA and IVA.
 
During the Treatment Period, study drug refers to VX-445/TEZ/IVA and matching placebo, TEZ/IVA and matching placebo, and IVA.
 
Active study drugs will be orally administered as fixed-dose combination (FDC) film-coated tablets (either VX-445/TEZ/IVA or TEZ/IVA) in the morning and as a film-coated IVA tablet in the evening.
 
Active substance: VX-445/TEZ (VX-661)/IVA (VX-770)

**Activity:** CFTR corrector, CFTR corrector, and CFTR potentiator  
**Strength:** 100 mg/50 mg/75 mg

[figure not shown]
**Active substance:** TEZ (VX-661)/ IVA (VX-770)  
**Activity:** CFTR corrector and CFTR potentiator  
**Strength:** 100 mg/150 mg

**Active substance:** IVA (VX-770)  
**Activity:** CFTR potentiator  
**Strength:** 150 mg

**Study Duration** The total study duration is approximately 36 weeks (4 weeks for the Screening Period, 4 weeks for the TEZ/IVA Run-in Period, 24 weeks for the Treatment Period, and 4 weeks for the Safety Follow-up Period).

**Study Design** This is a Phase 3b, randomized, double-blind, active-controlled, parallel-group, multicenter study (Figure 2-1).

**Figure 2-1 Schematic of the Study Design**

IVA: ivacaftor; N: number of subjects; TEZ: tezacaftor  
 Note: The Safety Follow-up Visit is not required for subjects who complete the Week 24 Visit and have enrolled in an open-label study within 28 days after the last dose of study drug.

In the TEZ/IVA Run-in Period, all subjects will receive TEZ 100 mg once daily (qd)/IVA 150 mg every 12 hours (q12h). After completing the TEZ/IVA Run-in Period, subjects will be randomized (1:1) to the VX-445/TEZ/IVA group or TEZ/IVA group for the Treatment Period (Table 2-1).

**Table 2-1 Treatment Period Groups and Dosages**

Treatment Group	VX-445 Dosage	TEZ Dosage	IVA Dosage
VX-445/TEZ/IVA	200 mg qd	100 mg qd	150 mg q12h
TEZ/IVA	0 mg qd	100 mg qd	150 mg q12h

IVA: ivacaftor; q12h: every 12 hours; qd: once daily; TEZ: tezacaftor  
 Randomization will be stratified by ppFEV1 determined during the TEZ/IVA Run-in Period (Day -14 assessment; <70 versus ≥70), age at the Screening Visit (<18 versus ≥18 years of age), and whether the subject is receiving CFTR modulator treatment at the Screening Visit (yes versus no). If the Day -14 ppFEV1 value is not valid or not

available, the most recent available ppFEV1 value will be used for stratification.

**Assessments Efficacy:** CFQ-R, spirometry

**PD:** SwCl

**Safety:** AEs, clinical laboratory assessments, ECGs, vital signs, pulse oximetry, ophthalmologic examinations, and physical examinations

**Statistical Analyses Statistical Methods/Analyses**

The baseline value, unless otherwise specified, will be defined as the most recent non-missing measurement collected before the first dose of study drug in the Treatment Period (i.e., the Day 1 Visit). The TEZ/IVA Run-in Period is intended to establish a reliable on-treatment (TEZ/IVA) baseline for comparison during the Treatment Period.

The primary efficacy endpoint is the absolute change in CFQ-R respiratory domain score from baseline through Week 24. The primary null hypothesis to be tested is that the mean absolute change in CFQ-R respiratory domain score from baseline through Week 24 is the same for the VX-445/TEZ/IVA and TEZ/IVA groups. The null hypothesis will be tested at a 2-sided significance level of 0.05.

Assuming a within-group SD of 18 and a treatment difference of 10 between VX-445/TEZ/IVA and TEZ/IVA, a sample size of 71 subjects completing the Treatment Period in each group for a total of 142 subjects will have approximately 90% power for the CFQ-R respiratory domain score hypothesis testing, based on a 2-sample t-test at a significance level of 0.05. Assuming a 10% dropout rate, up to approximately 158 subjects will be enrolled.

The primary analysis for CFQ-R will be based on a mixed-effects model for repeated measures (MMRM). The primary result obtained from the model will be the estimated treatment difference through Week 24. The treatment difference at each post-baseline visit, obtained from the model, will also be provided.

A hierarchical fixed-sequence testing procedure will be used to control the overall family-wise type I error for the testing of the primary endpoint and key secondary endpoint.

The safety endpoints include AEs, clinical laboratory values, ECGs, vital signs, and pulse oximetry through the Safety Follow-up Visit. The safety analysis will be descriptive only.

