**Table 3-2 Study VX18-445-109: Treatment Period and Safety Follow-up Visit**

Event/ Assessment a	TEZ/IVA Run-in Period (4 weeks)		Treatment Period (24 weeks)								ETT Visit b	Safety Follow-up Visit c (28 ± 7 Days After Last Dose of Study Drug)	Comments
	Day -28 ± 1 day	Day -14 (Day -15 to Day -3)	Day 1 d	Day 15 ± 3 days	Week 4 ± 5 days	Week 8 ± 5 days	Week 12 ± 5 days	Week 16 ± 5 days	Week 20 ± 5 days	Week 24 ± 5 days			
Clinic visit	X	X	X	X	X	X		X		X	X	X	
Telephone contact							X		X				Assess the subject's status, any AEs, concomitant medications, treatments, and procedures.
Inclusion and exclusion criteria confirmation	X												
CFQ-R			X		X	X		X		X	X	X	Completed before any other assessments scheduled at relevant visits (Section 11.4.1).
Weight and height	X		X	X	X	X		X		X	X	X	Measured with shoes off. Height will only be collected for subjects ≤21 years of age on the date of informed consent (Section 11.4.3).
Ophthalmologic examination										X	X		Subjects <18 years of age on the date of informed consent and who completed at least 12 weeks of study drug treatment will have a single ophthalmologic examination at either the ETT or Week 24 Visit, whichever comes first (Section 11.5.6).
Complete physical examination	X		X		X					X	X		Symptom directed physical examinations may be performed at any time if deemed necessary by the investigator (Section 11.5.3).

a All assessments will be performed before dosing unless noted otherwise.

b If a subject prematurely discontinues study drug treatment, an ETT Visit should be scheduled as soon as possible after the decision to discontinue treatment. Subjects who prematurely discontinue treatment during the Treatment Period will continue to complete all scheduled study visits for assessments following completion of the ETT Visit.

c The Safety Follow-up Visit is required for all subjects, unless the subject completes the Week 24 Visit and has enrolled in a separate open-label study within 28 days after the last dose of study drug. If an ETT Visit occurs 3 weeks or later following the last dose of study drug, then the ETT Visit replaces the Safety Follow-up Visit.

d To enter the Treatment Period, conditions for entry must be satisfied.

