#### **9.1.2 Tezacaftor/Ivacaftor Run-in Period**

The TEZ/IVA Run-in Period has a 4-week duration and is designed to establish a reliable on-treatment (TEZ/IVA) baseline for the Treatment Period. The first dose of open-label TEZ/IVA will be administered at the Day -28 Visit. The last dose of open-label TEZ/IVA will be administered in the evening on Day -1 (1 day before the Day 1 Visit).

The Day -14 spirometry assessment will be used for stratification of randomization to the Treatment Period (Section 9.2).

Subjects who prematurely discontinue study drug treatment during the TEZ/IVA Run-in Period will not be randomized or participate in the Treatment Period (Section 9.1.5.1).

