## **9.2 Method of Assigning Subjects to Treatment Groups**

Subjects will be randomized (1:1) to the VX-445/TEZ/IVA or TEZ/IVA group. Randomization will be stratified by ppFEV1 determined during the TEZ/IVA Run-in Period (Day -14 assessment; <70 versus ≥70), age at the Screening Visit (<18 versus ≥18 years of age), and whether the subject is receiving CFTR modulator treatment at the Screening Visit (yes versus no). If the Day -14 ppFEV1 value is not valid or not available, the most recent available ppFEV1 value will be used for stratification.

An interactive web response system (IWRS) will be used to assign subjects to treatment. The randomization code list will be produced by Vertex Biometrics or a qualified randomization vendor.

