#### **Power for Primary Efficacy Endpoint**

The primary efficacy endpoint is the absolute change in CFQ-R respiratory domain score from baseline through Week 24. The primary null hypothesis to be tested is that the mean absolute change in CFQ-R respiratory domain score from baseline is the same for the 2 treatment groups, VX-445/TEZ/IVA and TEZ/IVA. The null hypothesis will be tested at a 2-sided significance level of 0.05.

Assuming a within-group SD of 18 and a treatment difference of 10 between VX-445/TEZ/IVA and TEZ/IVA, a sample size of 71 subjects completing the Treatment Period in each group for a total of 142 subjects will have approximately 90% power for the CFQ-R respiratory domain score hypothesis testing, based on a 2-sample t-test at a significance level of 0.05 (2-sided). Assuming a 10% dropout rate, up to approximately 158 subjects will be enrolled.

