9 STATISTICAL ANALYSIS

9.1 General Considerations

Continuous variables will be summarized using the following descriptive summary statistics: the number of subjects (n), mean, SD, median, minimum value (min), and maximum value (max).

Categorical variables will be summarized using counts and percentages.

Baseline value, unless otherwise specified, will be defined as the most recent non-missing measurement (scheduled or unscheduled) collected before the first dose of study drug in the Treatment Period (i.e., the Day 1 Visit). For ECG, baseline will be defined as the most recent pretreatment measurement (or the average of triplicate measurements, if the most recent pretreatment measurement is obtained in triplicate) before the first dose of study drug in the Treatment Period (i.e., the Day 1 Visit).

Absolute change from baseline will be calculated as post-baseline value – baseline value.

Relative change from baseline will be calculated as (post-baseline value – baseline value)/baseline value.

The **Treatment-emergent (TE) Period for the Run-in Period** will be from the first dose of study drug in the Run-in Period to (1) the first dose of study drug in the Treatment Period for subjects who complete the Run-in Period and continue to the Treatment Period, or (2) 28 days after the last dose date of study drug in the Run-in Period or date of completion of study participation, whichever occurs first, for subjects who do not continue to the Treatment Period (e.g., subjects who do not meet the conditions to enter the Treatment Period).

The **TE Period for the Treatment Period** will include the time from the first dose date of study drug in the Treatment Period (ELX/TEZ/IVA or placebo + TEZ/IVA) to 28 days after the last dose of the study drug or to the date of completion of study participation, whichever occurs first.

Unscheduled visits: Unscheduled visit measurements will be included in analysis as follows:

- 1) In scheduled visit windows per specified visit windowing rules
- 2) In the derivation of baseline and last on-treatment measurements
- 3) In the derivation of maximum and minimum values during TE period, and maximum and minimum change from baseline values during TE period for safety analyses
- 4) In individual subject data listings as appropriate

Visit windowing rules: The analysis visit windows for protocol-defined visits are provided in [Appendix A](#).

Incomplete/missing data will not be imputed, unless specified otherwise.

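### The run-in schedules one on-treatment CFQ-R score and its Day -14 ppFEV1 and sweat chloride values stay out of the models: a low-cost precision gain, not an error or a power shortfall

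*Protocol*

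**What the plan says.** The synopsis (Statistical Methods/Analyses) gives the purpose of the run-in: "The TEZ/IVA Run-in Period is intended to establish a reliable on-treatment (TEZ/IVA) baseline for comparison during the Treatment Period". Protocol 9.1.2 and 9.3.1 repeat it.

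- **CFQ-R.** Tables 3-1 and 3-2 schedule it at Screening and Day 1, then at Weeks 4, 8, 16 and 24. There is none at Day -28 or Day -14.
- **Spirometry and sweat chloride.** Table 3-2 schedules both at Day -14 and Day 1. Protocol 9.1.2 gives the use of the first spirometry value: "The Day -14 spirometry assessment will be used for stratification of randomization to the Treatment Period". No analysis use is stated for Day -14 sweat chloride.
- **Baseline.** SAP 9.1 takes the "most recent non-missing measurement (scheduled or unscheduled) collected before the first dose of study drug in the Treatment Period". For CFQ-R, the baseline window in SAP Appendix A (Table 12-1) is day 1 or earlier, with no lower limit.
- **Models.** The CFQ-R MMRM (SAP 9.3.1.2) adjusts for continuous baseline ppFEV1, age group and modulator use at Screening. SAP 9.3.2.2 and 9.3.3.2 apply the same model to ppFEV1 and sweat chloride. So ppFEV1 is adjusted for its own baseline, while CFQ-R and sweat chloride are not.

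**The concern.** Every subject spends four weeks on TEZ/IVA to obtain a baseline, yet the primary endpoint has one scheduled reading from that time. The treatment estimate averages four post-baseline visits, so visit-level noise is averaged down after baseline but enters undiluted from the single Day 1 score, and the model has no CFQ-R covariate to absorb any of it.

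The single reading also leaves a gap. When Day 1 CFQ-R is missing and there is no unscheduled score, the most recent earlier score is the Screening one. For subjects who arrive on lumacaftor/ivacaftor or on no modulator, both of which protocol 9.3.1 expects, that score was not taken on TEZ/IVA. Spirometry and sweat chloride do not share this gap, because Day -14 stands in.

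At stake are the width of the confidence intervals and the integrity of a few CFQ-R baselines. CFQ-R matters most, because it is planned at about 90% power and ppFEV1 is tested only if CFQ-R succeeds.

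**Working it through.** **Inputs from the documents** (protocol 12.1 and 9.2; SAP 9.3.1.2)
- Test: two-sided, alpha 0.05.
- CFQ-R planning values: "Assuming a within-group SD of 18 and a treatment difference of 10 between VX-445/TEZ/IVA and TEZ/IVA".
- 71 completers per group: "a total of 142 subjects will have approximately 90% power for the CFQ-R respiratory domain score hypothesis testing".
- Equal allocation: "Subjects will be randomized (1:1) to the VX-445/TEZ/IVA or TEZ/IVA group".
- ppFEV1: SD 7, difference 5, stated power about 98%.
- Visits averaged: 4 for CFQ-R and ppFEV1, 3 for sweat chloride.

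**Step 1. The plan's own figures.** Two-sample t-test power (noncentral t) with 71 per group is 90.8% for CFQ-R and 98.8% for ppFEV1. Enrolment is 142/0.9 = 157.8, so 158. All three reproduce.

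**Step 2. Variance model (assumed).** Let r be the correlation between any two visits, m the number of post-baseline visits averaged and p the number of baseline readings. In units of the single-visit variance:
- change score: C(p) = (1+(m-1)r)/m + (1+(p-1)r)/p - 2r
- adjusted for the endpoint's own baseline readings: A(p) = (1+(m-1)r)/m - p·r²/(1+(p-1)r)

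Under this model, averaging two baseline readings and entering both as covariates give the same A(2).

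**Step 3. CFQ-R, unadjusted change score (m = 4).** C(1) = 1.25(1-r) and C(2) = 0.75(1-r), so the ratio is 0.60 for any r. If 18 is the SD of the four-visit average change from one baseline, it becomes 18·√0.60 = 13.9, and power at 71 per group rises from 90.8% to 98.9%. True between-subject variation in response erodes this. If it makes up a share h of the variance, the SD is 18·√(h + 0.6(1-h)):

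| h | SD | Power |
|---|---|---|
| 0 | 13.9 | 98.9% |
| 0.25 | 15.1 | 97.6% |
| 0.50 | 16.1 | 95.7% |
| 0.75 | 17.1 | 93.4% |

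**Step 4. CFQ-R with Day 1 CFQ-R as a covariate.** This separates the value of the second reading from the value of adjustment. The SD is 18·√(A/C(1)).

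| r | C(1) | A(1) | A(2) | A(2)/A(1) | Power, Day 1 only | Power, both |
|---|---|---|---|---|---|---|
| 0.4 | 0.750 | 0.390 | 0.321 | 0.82 | 99.5% | 99.9% |
| 0.5 | 0.625 | 0.375 | 0.292 | 0.78 | 98.9% | 99.8% |
| 0.7 | 0.375 | 0.285 | 0.199 | 0.70 | 96.5% | 99.5% |

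The second reading therefore cuts residual variance by a further 18-30%. In scenarios where correlation decays with time (a subject effect, an exponentially decaying component and independent error, with the Day -14 visit 2 or 0.5 weeks before Day 1), the further cut was about 6-18%.

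**Step 5. ppFEV1 (Day 1 value already a covariate).** Adding Day -14 multiplies the SD by √(A(2)/A(1)), which is 0.88 at r = 0.5 and 0.79 at r = 0.9. If 7 is the adjusted SD, it becomes 6.2 to 5.6 and power moves from 98.8% to 99.8-99.96%.

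**Step 6. Sweat chloride (m = 3, own baseline not listed as a covariate).** Relative to the planned change score, entering both readings multiplies the SD by √(A(2)/C(1)), which is 0.71 at r = 0.5 and 0.78 at r = 0.9. Day 1 alone gives 0.79 and 0.96. No SD or power is stated for this endpoint.

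**The case against.** The strongest reply is that nothing is broken. On-treatment baseline can simply mean that everyone is measured on TEZ/IVA, whatever they arrived on, and a Day 1 value after four weeks does that. The documents never promise replicate readings. Planned power is met. ppFEV1 is already adjusted for its baseline, and each sweat chloride value is already the mean of two arms. Sweat chloride is also outside the testing hierarchy and has only a nominal P value. All of this stands.

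It is also true that much of the apparent CFQ-R gain comes from adjusting for the Day 1 score, which needs no new data. By step 4, the second reading then adds only about 0.4 to 3 points of power.

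Replacing the Day 1 baseline with an average would have a drawback. Protocol 9.5 aligns Day 1 with the inhaled-antibiotic cycle, whereas the Day -14 window runs from Day -15 to Day -3. Averaging would also shift the within-group changes that are reported. Entering both values as covariates avoids redefining those changes.

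Some subjects new to TEZ/IVA, or switching from lumacaftor/ivacaftor, may still be changing at Day -14. Randomisation balances this in expectation, so it can shrink the gain but does not bias the comparison.

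The reply does not cover two things: the fallback of a missing Day 1 CFQ-R to a pre-run-in score, and the absence from the models of Day -14 values that are already collected.

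**Conclusion.** The point holds as an efficiency improvement, plus one small gap in the CFQ-R baseline rule.

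A reader might infer that the run-in fails its stated purpose, that the trial is underpowered, or that a 40% variance cut is there for the taking. The documents support none of these. The purpose can be read as met by Day 1, and the stated power reproduces. The 40% figure needs equal correlation at all lags, no variation in true response, an unadjusted change score, and 18 read as the SD of the four-visit average change. A reader might also infer that the Day -14 values go unused, but ppFEV1 defines a stratum and both are fallbacks.

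The fair size for a second CFQ-R reading, after Day 1 adjustment, is a residual variance cut of about 18-30% under equal correlation of 0.4-0.7, or about 6-18% with decay. For ppFEV1 and sweat chloride the gain is narrower intervals, with no realistic change in a test result. The direction was the same in every scenario examined. The size rests on assumed correlations.

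The documents do not show how often Day 1 CFQ-R would be missing, so the effect of the Screening fallback cannot be sized.

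**What to change.** 1. **SAP 9.3.2.2 and 9.3.3.2.** Keep Day 1 as baseline and enter the endpoint's own Day -14 and Day 1 values as covariates. For sweat chloride this also brings its own baseline into the model. State a rule for a missing Day -14 value so that no subject drops out of the model, and show the Day 1-only result as a sensitivity analysis. The cost is SAP wording only: no new data, and reported within-group changes remain defined from Day 1. SAP section 4 allows such an amendment before database lock and unblinding.
2. **Protocol Table 3-2, SAP 9.1 and 9.3.1.2.** For subjects who have still to pass Day -14, add CFQ-R as the first assessment of that visit. Use it as the baseline when Day 1 is missing, and enter it with Day 1 CFQ-R as a covariate in the primary MMRM. The same rule for a missing Day -14 score is needed for subjects already past that visit. The cost is a protocol amendment and one more questionnaire at an existing clinic visit, plus the Parent version for ages 12-13. The SAP already provides for CFQ-R collected at home because of COVID-19, so collection may be well advanced and this part may reach few subjects.
3. **If part 2 comes too late.** Adding Day 1 CFQ-R to the primary MMRM still captures much of the gain and needs no new data.

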### **3 SCHEDULE OF ASSESSMENTS**

Schedules of assessments are in [Table 3-1](#) and [Table 3-2](#).

All visits are to be scheduled relative to the Day 1 Visit (first dose of randomized study drug in the Treatment Period). For example, the Week 4 ( $\pm 5$  days) Visit would occur after 4 weeks of study drug administration in the Treatment Period has been completed.

The Cystic Fibrosis Questionnaire–Revised (CFQ-R) must be completed before any other assessment (except signing of ICF) at relevant clinic visits. Remaining assessments may be performed in any order when more than 1 assessment is required at a particular time point. All assessments will be performed before study drug dosing (Section [9.6.1](#)), unless noted otherwise.

**Table 3-1 Study VX18-445-109: Screening**

Event/Assessment	Screening Visit Day -56 to Day -29	Comments
ICF and assent (when applicable)	X	
Inclusion and exclusion criteria review	X	
Demographics	X	
Medical history	X	
CFQ-R	X	Completed before the start of any other assessments (except signing ICF) scheduled for that visit.
CFTR genotype	X	If the screening CFTR genotype result is not received before enrollment, a previous CFTR genotype laboratory report may be used to establish eligibility. Subjects who have been enrolled and whose screening genotype does not confirm eligibility must be discontinued from the study.
FSH	X	Measured for any suspected postmenopausal female with at least 12 months of continuous spontaneous amenorrhea.
Serum pregnancy test (all female subjects)	X	
Hematology	X	
Coagulation	X	
Serum chemistry	X	
Urinalysis	X	
Weight and height	X	Measured with shoes off.
Ophthalmologic examination	X	Only conducted for subjects who are <18 years of age on the date of informed consent.
Complete physical examination	X	
Vital signs and pulse oximetry	X	Collected after the subject has been at rest for at least 5 minutes.
Standard 12-lead ECG	X	Performed after the subject has been at rest for at least 5 minutes.
Spirometry	X	Performed pre- or post-bronchodilator.
Medications review	X	
Sweat chloride	X	
AEs and SAEs	Continuous from signing of ICF through Safety Follow-up Visit	
AE: adverse event; CFQ-R: Cystic Fibrosis Questionnaire-Revised; FSH: follicle stimulating hormone; ICF: informed consent form; SAE: serious adverse event		

